4.4.2 Immunogenicity

4.4.2.1 Computed Values for Analysis

In order to appropriately manage extreme values (undetectable responses < the lower limit of quantitation [LLOQ] and \geq the upper limit of quantitation [ULOQ]) for analysis purposes, the following computational rule is applied to the values provided in the clinical database for each blood sample drawn:

- If a value is < LLOQ, then use the computed value LLOQ/2
- If a value is between \geq LLOQ and < ULOQ, then use the value
- If a value is \geq ULOQ, then use the computed value ULOQ

4.4.2.2 Seroprotection

If the computed value is \geq to a predefined cutoff, then the derived seroprotection indicator will be "Yes" for that test, otherwise seroprotection will be "No". Note: If the computed value is missing, seroprotection will be missing.

hSBA vaccine seroprotection is defined as: hSBA titers \geq 1:8.

4.4.2.3 Fold-rise

The derived endpoint fold-rise is driven by both baseline and post-baseline computed values and is computed as follows:

- Calculate the fold-rise of values as the ratio of post-baseline computed value divided by baseline computed value

Note: If baseline or post-baseline is missing, then fold-rise is missing.

4.4.2.4 Seroconversion

If the computed value is \geq 4-fold rises, then the derived \geq 4-fold rises indicator will be "Yes" for that test, otherwise \geq 4-fold rises will be "No".

Note: If baseline or post-baseline is missing, then fold-rise is missing.

Using the calculation method described in [section 4.4.2.3](#), the \geq 4-fold rises indicator evaluated after the last dose in infancy for hSBA titers and rSBA titers will be derived as follows:

- Using values of BL0002 (Visit 3 for Groups 1, 2, 3 and Visit 4 for Groups 4) as post-baseline values and values of BL0001 (Visit 1 for all groups) as baseline values.

For the booster series, two \geq 4-fold rises indicators for hSBA and rSBA titers will be presented and derived as follows:

- Using values of BL0004 (Visit 5 for Groups 1, 2, 3 and Visit 6 for Groups 4) as post-baseline values and values of BL0001 (Visit 1 for all groups) as baseline values.
- Using values of BL0004 (Visit 5 for Groups 1, 2, 3 and Visit 6 for Groups 4) as post-baseline values and values of BL0003 (Visit 4 for Groups 1, 2, 3 and Visit 5 for Groups 4) as baseline values.

4.4.2.5 hSBA Vaccine Seroresponse

hSBA vaccine seroresponse for serogroups A, C, Y, and W is defined as either:

- For a subject with a pre-vaccination titer $<$ 1:8, the post-vaccination titer must be \geq 1:16;
- For a subject with a pre-vaccination titer \geq 1:8, the post-vaccination titer must be at least 4-fold greater than the pre-vaccination titer.

For the vaccine seroresponse evaluated after the last dose in infancy, the post-vaccination titer corresponds to BL0002 (Visit 3 for Groups 1, 2, 3 and Visit 4 for Groups 4) and the pre-vaccination titer corresponds to BL0001 (Visit 1 for all groups).

For the vaccine seroresponse evaluated after the booster dose, two seroresponse indicators will be defined as follows:

- The post-vaccination titer corresponds of BL0004 (Visit 5 for Groups 1, 2, 3 and Visit 6 for Groups 4) and the pre-vaccination titer corresponds to BL0001 (Visit 1 for all groups).
- The post-vaccination titer corresponds of BL0004 (Visit 5 for Groups 1, 2, 3 and Visit 6 for Groups 4) and the pre-vaccination titer corresponds to BL0003 (Visit 4 for Groups 1, 2, 3 and Visit 5 for Groups 4).

4.4.2.6 Pertussis vaccine seroresponse for anti-PT and anti-FHA

For Groups 1, 2, and 3, 30 days after Dose 2 in infancy, Pertussis vaccine seroresponse for anti-PT and anti-FHA is defined as:

- If the pre-primary vaccination concentration is $< 4 \times \text{LLOQ}$, post-primary vaccination concentration $\geq 4 \times \text{LLOQ}$
- If the pre-primary vaccination concentration is $\geq 4 \times \text{LLOQ}$, post-primary vaccination concentration \geq pre-primary vaccination concentration

For Groups 1, 2, and 3, before and 30 days after the booster dose (Dose 3) and for Group 4, before and 30 days after the booster dose (Dose 4), Pertussis vaccine seroresponse for anti-PT and anti-FHA is defined as:

- If the pre-booster vaccination concentration is $< 4 \times \text{LLOQ}$, post-booster vaccination concentration $\geq 4 \times$ pre-booster concentration
- If the pre-booster vaccination concentration is $\geq 4 \times \text{LLOQ}$, post-booster vaccination concentration $\geq 2 \times$ pre-booster concentration

4.4.2.7 rSBA Vaccine Seroresponse

rSBA vaccine seroresponse for serogroups A, C, Y, and W is defined as either:

- For a subject with a pre-vaccination titer $< 1:8$, the post-vaccination titer must be $\geq 1:32$;
- For a subject with a pre-vaccination titer $\geq 1:8$, the post-vaccination titer must be at least 4-fold greater than the pre-vaccination titer.

For the vaccine seroresponse evaluated after the last dose in infancy, the post-vaccination titer corresponds to BL0002 (Visit 3 for Groups 1, 2, 3 and Visit 4 for Groups 4) and the pre-vaccination titer corresponds to BL0001 (Visit 1 for all groups).

For the vaccine seroresponse evaluated after the booster dose, two seroresponse indicators will be defined as follows:

- The post-booster vaccination titer corresponds of BL0004 (Visit 5 for Groups 1, 2, 3 and Visit 6 for Groups 4) and the pre-primary vaccination titer corresponds to BL0001 (Visit 1 for all groups).
- The post- booster vaccination titer corresponds of BL0004 (Visit 5 for Groups 1, 2, 3 and Visit 6 for Groups 4) and the pre- booster vaccination titer corresponds to BL0003 (Visit 4 for Groups 1, 2, 3 and Visit 5 for Groups 4).

4.4.3 Efficacy

Not applicable.

4.4.4 Derived Other Variables

4.4.4.1 Age for Demographics

The age of a subject in the study is the calendar age in day at the time of inclusion. Age will also be presented using a categorical variable with two categories: ≥ 42 to ≤ 59 days and ≥ 60 to 89 days.

4.4.4.2 Duration of the Study

The duration is computed in days as follows: Latest period date - earliest period date + 1.

4.4.4.3 Subject Duration

The duration of a subject participation in the study is computed as follows:

Maximum (Visit dates, Termination date, Last contact date) – V01 date + 1.

5 Statistical Methods and Determination of Sample Size

The statistical analyses will be performed under the responsibility of the Sponsor's Biostatistics platform using SAS® Version 9.4 software or later.

For descriptive purposes, the following statistics in [Table 5.1](#) will be presented. The confidence interval (CI) for the single proportion will be calculated using the exact binomial method (Clopper-Pearson method), quoted by Newcombe [\(1\)](#).

For immunogenicity results, assuming that Log₁₀ transformation of the titers / data follows a normal distribution, at first, the mean and the 95% CI will be calculated on Log₁₀ (titers / data) using the usual calculation for normal distribution (using Student's t distribution with n-1 degree of freedom), then antilog transformations will be applied to the results of calculations, in order to provide geometric means (GMs) and their 95% CI.

The results of the statistical analysis will be available in the final clinical study report (CSR).

Table 5.1: Descriptive statistics produced

Baseline characteristics and follow-up description	Categorical data	Number of subjects. Percentage of subjects.
	Continuous data	Mean, standard deviation, quartiles, minimum, and maximum.
Clinical safety results	Categorical data	Solicited: Number and percentage (95% CIs) of subjects. Unsolicited: Number and percentage (95% CIs) of subjects, and number of events.
Immunogenicity results	Categorical data (seroprotection, seroconversion, cutoff)	Number and percentage (95% CIs) of subjects.
	Continuous data (titer / data)	Log10: Mean and standard deviation. Anti-Log10 (work on Log10 distribution, and anti-Log10 applied): Geometric mean, 95% CI of the geometric mean, quartiles, minimum, and maximum. Graphical representation by Reverse Cumulative Distribution Curve (RCDC).

The CI for the single proportion will be calculated using the exact binomial method (Clopper-Pearson method), quoted by Newcombe [\(1\)](#), ie, using the inverse of the beta integral with SAS®.

For immunogenicity results, assuming that Log10 transformation of the titers / data follows a normal distribution, at first, the mean and the 95% CI will be calculated on Log10 (titers / data) using the usual calculation for normal distribution (using Student's t distribution with n-1 degree of freedom), then antilog transformations will be applied to the results of calculations, in order to provide geometric means (GMs) and their 95% CI.

5.1 Statistical Methods

5.1.1 Hypotheses and Statistical Methods for Primary Objective(s)

5.1.1.1 Hypotheses

Non-inferiority of MenACYW conjugate vaccine (Group 1) compared to Nimenrix® (Group 2) in terms of hSBA antibody titers after a 3-dose series to infants and toddlers will be tested.

For each of the 4 serogroups (A, C, W, and Y), GMTs 30 days after a 3- dose series vaccination will be used to compare Group 1 and Group 2 with the following individual hypotheses:

H_0 (*Null hypothesis*):

- $GMT_{MenACYW} / GMT_{Nimenrix} \leq 1/1.5$ (or $GMT_{Nimenrix} / GMT_{MenACYW} \geq 1.5$)

H_1 (*Alternative hypothesis*):

- $GMT_{MenACYW} / GMT_{Nimenrix} > 1/1.5$ (or $GMT_{Nimenrix} / GMT_{MenACYW} < 1.5$)

5.1.1.2 Statistical Methods

Assuming that Log10 transformation of the data follows a normal distribution, the Log10(data) will be used for the statistical analysis, then antilog transformations will be applied to the results of calculations, in order to provide the results in terms of GMT.

The statistical methodology will be based on the use of the 2-sided 95% confidence interval (CI) of the ratio of post-vaccination GMTs between Group 1 and Group 2. The CI will be calculated using a normal approximation of log-transformed titers.

Non-inferiority will be demonstrated if all 4 individual null hypotheses (4 serogroups) are rejected. For each serogroup, the 2-sided 95% CI of the GMT ratio Group 1 (MenACYW) / Group 2 (Nimenrix) should lie above 1/1.5

5.1.2 Hypotheses and Statistical Methods for Secondary Objective 1

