2.3 Observational Objectives

Immunogenicity

To describe the antibody responses against meningococcal serogroups A, C, W, and Y measured by rSBA in a subset of subjects when MenACYW conjugate vaccine or Nimenrix® is administered concomitantly with routine pediatric vaccines (all groups)

Safety

To describe the safety profile of MenACYW conjugate vaccine and Nimenrix® when administered concomitantly with routine pediatric vaccines in healthy infants and toddlers

The endpoints for the observational objectives are presented in [Section 9.3.2.2](#).

3 Investigators and Study Organization

This study will be conducted in approximately 50 centers in Europe. The Principal Investigators and any sub-investigators at the individual sites will be coordinated by 1 Coordinating Investigator in each country. Details of the study centers, the Investigators at each center, and the Coordinating Investigators are provided in the “List of Investigators and Centers Involved in the Trial” document.

The Sponsor’s Responsible Medical Officer (the RMO, the person authorized to sign this protocol and any amendments on behalf of the Sponsor) is [REDACTED]
[REDACTED].

4 Independent Ethics Committee / Institutional Review Board

Before the investigational product can be shipped to the investigational site and before the inclusion of the first subject, this protocol, the informed consent form (ICF), subject recruitment procedures, and any other written information to be provided to subjects must be approved by, and / or receive favorable opinion from, the appropriate Independent Ethics Committees (IECs) or Institutional Review Boards (IRBs).

In accordance with Good Clinical Practice (GCP) and local regulations, each Investigator and / or the Sponsor are responsible for obtaining this approval and / or favorable opinion before the start of the study. If the protocol is subsequently amended, approval must be re-obtained for each substantial amendment. Copies of these approvals, along with information on the type, version number, and date of document, and the date of approval, must be both maintained by the Investigator and the Sponsor together with the composition of the IEC / IRB (the names and qualifications of the members attending and voting at the meetings).

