5.1.4 Visit Procedures

Visit 1 (D0; 2 months [6 to 12 weeks] of age): Inclusion, Randomization, Blood Sample, and Vaccination

- 1) Give the subject's parent / legally acceptable representative information about the study, obtain written informed consent, and give him / her a signed copy.
- 2) Check inclusion and exclusion criteria for eligibility. Review vaccination history from the child's immunization record.
- 3) Collect demographic data (including birth weight and gestational age).
- 4) Obtain verbal medical history about the subject, including ongoing medication.
- 5) Conduct a physical examination as per standard of care. Perform a physical examination, including, but not limited to, examination of the head (ear, nose, and throat), neck, heart, lungs, abdomen, and extremities. If a routine examination had been performed within the last week by the Investigator, a sub-investigator, or a licensed nurse practitioner, it does not need to be repeated unless there were some changes in health status, in which case it may be limited to the affected area.
- 6) Take the subject's temperature (Refer to [Section 9.3.2.3.2](#) for accurate temperature assessment). If the temperature is $\geq 38^{\circ}\text{C}$, postpone vaccination until the condition is resolved.
- 7) Take the subject's weight to determine if 2 or 3 ml are to be collected for BL0001 (refer to the Operating Guidelines for further instructions).
- 8) Contact the interactive response technology (IRT) system for vaccine group randomization (at least allocation of subject number, dose number of all vaccines).
- 9) Review temporary contraindications for blood sampling. Ensure the subject has not had any antibiotics within the previous 72 hours (3 days).
- 10) Collect 2 or 3 mL of blood (BL0001) depending on the weight of the subject at inclusion from all subjects including those subjects in the rSBA subset (see [Section 7.1](#) for detailed instructions regarding the handling of blood samples and [Section 6.5](#) for more details on the rSBA subset). If attempts to obtain the first blood draw are unsuccessful (after reasonable attempts as per local regulations) either the Visit 1 can be rescheduled to a later date at which point inclusion/exclusion criteria must be re-validated or the subject will be withdrawn from the study without being vaccinated. If during the rescheduled visit the first blood draw cannot be obtained, the subject will be withdrawn from the study without being vaccinated.

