6.5 Randomization and Allocation Procedures

On the day of enrollment, subjects who meet the inclusion/exclusion criteria and whose parent / legally acceptable representative sign the ICF will be randomly assigned to Groups 1 through 4. Countries where PCV10 will be administered for pneumococcal vaccination, 1432 subjects will be randomized in a 1:1 ratio to 2 groups such that Groups 1 and 2 will have approximately 716 subjects each; and countries where PCV13 will be administered for pneumococcal vaccination, 220 subjects will be randomized in a 1:1 ratio to 2 groups such Groups 3 and 4 will have approximately 110 subjects each.

Randomization will be performed with permuted block method with stratification by center and age categories as follows: approximately 6 to 8 weeks (≥ 42 to ≤ 59 days), and 9 to 12 weeks (≥ 60 to ≤ 89 days).

^a All unexpected and related SAEs submitted to EU competent authorities must be unblinded.

The IRT system will also be used to allocate subjects in the rSBA subset in the countries included in the subsets as follows:

- 100 subjects randomized to Group 1; 100 subjects randomized to Group 2
- 50 subjects randomized to Group 3; 50 subjects randomized to Group 4

The rSBA subset will include subjects from all countries except Poland.

The vaccination / site staff will connect to the IRT system, enter the identification and security information, and confirm a minimal amount of data in response to IRT system prompts. The IRT system will then provide at least the vaccine dose number (except for the rotavirus vaccine) and subject number. The full detailed procedures for group allocation are described in the Operating Guidelines. If the subject is not eligible to participate in the study, then the information will only be recorded on the subject recruitment log.

Subject numbers that are assigned by the IRT system will consist of a 12-digit string (a 3-digit country identifier, a 4-digit study center identifier, and a 5-digit subject identifier). For example, Subject 724000100005 is the fifth subject enrolled in Center Number 1 in Spain (724 being the Spain country code).

Subject numbers should not be reassigned for any reason. The randomization codes will be kept securely in the IRT system.

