9.1.2.2 Immunogenicity Assessment Methods

All assays will be performed at GCI, Swiftwater, PA or at qualified contract laboratories for GCI. For all samples, hSBA analysis will be done for all 4 serogroups.

Antibodies to meningococcal antigens (hSBA Method)

Functional meningococcal antibody activity against serogroups A, C, W, and Y will be measured in hSBA. Two-fold dilutions of test sera are prepared in sterile 96-well microtiter plates. Serogroup-specific meningococcal bacteria along with human complement are added to the serum dilutions and allowed to incubate. After this incubation period, an agar overlay medium is added to the serum/complement/bacteria mixture, allowed to harden, and then incubated overnight at 37°C with 5% carbon dioxide (CO₂). Bacterial colonies present in the wells are then counted. The endpoint titer is determined by the reciprocal serum dilution yielding $\geq 50\%$ killing as compared to the mean of the complement control wells. The lower limit of quantitation (LLOQ) of the hSBA assay is a titer of 1:4. This method will be performed on all blood samples (refer to [Table 9.1](#) and [Table 9.2](#)) for all study groups. In the event of insufficient serum sample volume, the conduct of the hSBA assay is of higher priority than the rSBA assay and the assays for antigens of concomitant vaccines.

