12.1.2 Hypotheses and Statistical Methods for Secondary Objectives

12.1.2.1 Hypotheses for Secondary Objective 1

If the primary objective is met, non-inferiority of MenACYW conjugate vaccine (Group 1) compared to Nimenrix® (Group 2) in terms of hSBA antibody titers $\geq 1:8$ after a 2-dose series in infants will be tested (Secondary Objective 1).

For each of the 4 serogroups (A, C, W, and Y), the percentages of subjects who achieve an hSBA titer $\geq 1:8$ 30 days after the 2 dose administered in infancy will be used to compare responses between Group 1 and Group 2 with the following individual hypotheses:

- H_0 (*Null hypothesis*): $p_{(MenACYW)} - p_{(Nimenrix)} \leq -10\%$
- H_1 (*Alternative hypothesis*): $p_{(MenACYW)} - p_{(Nimenrix)} > -10\%$

where $p_{(MenACYW)}$ and $p_{(Nimenrix)}$ are the percentages of subjects who achieve an hSBA titer $\geq 1:8$ in the MenACYW conjugate vaccine group and the Nimenrix® group, respectively.

12.1.2.2 Statistical Methods for Secondary Objective 1

Non-inferiority will be demonstrated if all 4 individual null hypotheses (4 serogroups) are rejected. If the lower limit of the 2-sided 95% CI of the difference between the 2 percentages is $> -10\%$, the non-inferiority will be demonstrated. The CI of the difference in percentages will be computed using the Wilson score method without continuity correction.

12.1.2.3 Hypotheses for Secondary Objectives 2, 3, 4, 5, 6 and 7

No hypotheses will be tested.

12.1.2.4 Statistical Methods for Secondary Objectives 2, 3, 4, 5, 6 and 7

The statistical analyses for the Secondary Objectives 2, 3, 4, 5, 6 and 7 will be descriptive.

In general, categorical variables will be summarized and presented by frequency counts, percentages, and CIs. The 95% CIs of point estimates will be calculated using the normal approximation for quantitative data and the exact binomial distribution (Clopper-Pearson method) for proportions. For GMTs and geometric mean concentrations (GMCs), 95% CIs of point estimates will be calculated using a normal approximation assuming they are log-normally distributed.

Reverse cumulative distribution curve (RCDC) figures may be also provided.

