3.2 Trial Plan

Approximately 1652 healthy infants aged 6 to 12 weeks at enrollment were to be randomized. Approximately 20% of subjects 6 to 8 weeks of age (≥ 42 to ≤ 59 days) should have been enrolled in Groups 1 and 2 to provide safety and immunogenicity data for this population, as described below:

- Group 1 and Group 2: approximately 144 subjects in each group.
- Group 3 and Group 4: approximately 22 subjects in each group.

The vaccination and blood sampling schedules are detailed in [Table 3.1](#) and [Table 3.2](#). A detailed summary of study procedures and assessments is provided in [Table 3.3](#) for Group 1, 2 and 3 and [Table 3.4](#) for Group 4.

Vaccinations

Healthy infants were randomized as follows depending on the pneumococcal vaccines that are administered in the respective countries.

Countries where the pneumococcal vaccination administered is PCV10 (Czech Republic, Romania, Sweden, Finland, and Poland): 1432 subjects were to be randomized in a 1:1 ratio to one of the following 2 groups:

- Group 1: MenACYW conjugate vaccine (3 doses) (2+1 regimen) + PCV10 + Hexavalent vaccine + MMR vaccine (n=716)
- Group 2: Nimenrix[®] (3 doses) (2+1 regimen) + PCV10 + Hexavalent vaccine + MMR vaccine (n=716)

Countries where the pneumococcal vaccination administered is PCV13 (Italy and Spain):

220 subjects were to be randomized in a 1:1 ratio to one of the following 2 groups:

- Group 3: MenACYW conjugate vaccine (3 doses) (2+1 regimen) + PCV13 + Hexavalent vaccine + MMR vaccine (n=110)
- Group 4: MenACYW conjugate vaccine (4 doses) (3+1 regimen) + PCV13 + Hexavalent vaccine + MMR vaccine (n=110)

For all 4 vaccine groups, the MMR vaccine may have been preferably administered concomitantly with the other vaccines at 12 to 18 months of age. If not, the subject should have received a licensed Measles, Mumps and Rubella vaccine with a gap of at least 4 weeks before any study vaccines or after the end of the study (ie, after the subject has completed the last study procedure at the last study visit). When administered outside the study visits, the licensed Measles, Mumps and Rubella vaccine were sourced by the health care system, according to the national immunization program.

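### Both confirmatory confidence intervals leave out the randomisation strata, and the primary one also leaves out the Day 0 titer: they are valid, but a little power is given up

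*SAP*

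**What the plan says.** Protocol 6.5 states: "Randomization will be performed with permuted block method with stratification by center and age categories as follows". The age categories are 42-59 and 60-89 days.

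The primary objective compares hSBA GMTs 30 days after the third dose, with a margin of 1/1.5 that all four serogroups must clear. On the interval, SAP 5.1.1.2 says "The CI will be calculated using a normal approximation of log-transformed titers", as does Protocol 12.1.1.2. For Secondary Objective 1 (titer of at least 1:8 after dose 2, margin 10 percentage points), Protocol 12.1.2.2 and SAP 5.1.2.2 say "The CI of the difference in percentages will be computed using the Wilson score method without continuity correction". Neither method names a stratum or covariate.

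The Day 0 titer is available. Protocol 9.1.2.2 says "For all samples, hSBA analysis will be done for all 4 serogroups", and the Visit 1 procedures in Protocol 5.1.4 say "If during the rescheduled visit the first blood draw cannot be obtained, the subject will be withdrawn from the study without being vaccinated". Age category enters the comparison only as a subgroup display (SAP 5.1.6.2). Center does not enter. The changes listed in SAP 5.7 touch neither interval.

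**The concern.** Balancing on center and age lowers the true variance of the group difference if those factors predict the response. An interval built on the full SD does not credit that reduction, so it is wider than it needs to be. A prognostic Day 0 titer would narrow it further at no data cost.

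This cannot produce a false success; it can only cause a missed one. The exposure is greatest if serogroup A or C, with the largest assumed SD (0.7), has a true ratio a little below 1, because one failing serogroup fails the objective. Secondary Objective 1 starts from less slack, with 90% stated power.

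**Working it through.** **Inputs.** From SAP 5.5: SD of log10 titer 0.7 (A, C), 0.5 (Y), 0.6 (W); 716 enrolled and 528 evaluable per group; one-sided alpha 2.5%; dose-2 rates 76, 94, 71 and 82% (A, C, Y, W). The margin is log10(1.5) = 0.1761. Assumed: R-squared from 0 to 10%, and independent serogroups.

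**Reproducing the plan.** SE = SD x sqrt(2/528), which is 0.0431 for SD 0.7. Power per serogroup is 98.3% (A), 98.3% (C), 99.99% (Y) and 99.75% (W), and the product is 96.4%. The stated 96.2% follows from rounded entries: 0.983 x 0.983 x 0.999 x 0.997 = 0.962. For Secondary Objective 1 the Farrington-Manning formula gives 90.5% against the stated 90%. The planned power therefore does not rely on adjustment.

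**Error of the unadjusted primary interval.** Stratified allocation removes stratum variance, apart from what random loss (528 of 716 remaining) puts back. The true variance is the nominal one times f = 1 - R2 + R2 x (1 - 528/716). One-sided error is 1 - Phi(1.96/sqrt(f)): 2.5, 2.4, 2.3 and 2.1% at R2 of 0, 2, 5 and 10%. A simulation with 40 balanced centers and no loss gave 2.4, 2.2 and 2.1% at 0, 5 and 10%, and 2.4-2.6% for the center-adjusted interval.

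**Primary power, age + country model.** Unadjusted: true variance scaled by f, interval built on the full SD. Adjusted: SE x sqrt(1 - R2) x 1.0007. The last factor is the cost of the extra terms, from 1,500 simulated trials (40 uneven centers in 5 countries, 20/80 age split, blocks of 4, random loss to 73.7%).

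| R2 of age + country | CI width | Ratio 1 in all | Ratio 0.9 in A only | Ratio 0.9 in all four |
|---|---|---|---|---|
| 0% | +0.07% | 96.4 to 96.4% | not computed | not computed |
| 2% | -0.9% | 96.6 to 96.8% | 84.2 to 84.7% | 68.6 to 69.6% |
| 5% | -2.5% | 96.8 to 97.3% | 84.6 to 86.0% | 69.3 to 71.8% |
| 10% | -5.1% | 97.1 to 98.0% | 85.2 to 88.0% | 70.4 to 75.5% |

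Example, serogroup A at 10% and ratio 0.9. The distance to the margin is 0.1761 - 0.0458 = 0.1303, or 3.03 SEs. Unadjusted: (3.03 - 1.96)/sqrt(0.926) = 1.10, giving 86.5%. Adjusted: 3.03/0.949 - 1.96 = 1.22, giving 89.0%. Multiplying by the other three serogroups gives 85.2% and 88.0%.

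**Center terms instead of country.** With about 40 unpooled centers (assumed; Protocol Section 3 says "This study will be conducted in approximately 50 centers in Europe", for all groups) the interval is 0.6% wider at R2 = 0 and 0.4, 1.9 and 4.5% narrower at 2, 5 and 10%, with power 96.6, 97.1 and 97.9%. If half of a 10% R2 lies between centers within country, age + country narrows the interval by 2.5% against 4.5% with center terms, and its power goes from 97.1 to 97.6%.

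**Day 0 titer alone.** At 2, 5 or 10% explained, power goes from 96.4% to 96.7, 97.2 or 98.0%. If it explains nothing, the age + country + baseline interval is 0.12% wider.

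**Secondary Objective 1.** 40,000 runs per serogroup, 5 equal countries x 2 age categories, random loss to 73.7%:

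| Strata R2 | Crude Wilson-based | Stratified Miettinen-Nurminen | Change (points) |
|---|---|---|---|
| 0% | 90.7% | 90.4% | -0.3 |
| 2% | 91.0% | 91.1% | +0.1 |
| 5% | 91.3% | 92.1% | +0.8 |
| 10% | 91.8% | 93.4% | +1.6 |

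One-sided error at a true difference of -10% was 2.2-2.6% (crude) and 2.4-2.6% (stratified). A stratified Newcombe-Wilson form with Mantel-Haenszel weights did not help: half-width 0.1-0.3% wider for A, Y and W, and 0.8-1.9% wider for C.

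**The case against.** The plan contains no error: both intervals hold their level and the stated power reproduces without adjustment. The gain at a true ratio of 1 is under one point. At SD 0.7 the lowest observed ratio that passes moves only from 0.810 to 0.802 at an R-squared of 10%.

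That 10% is also demanding. It implies a between-stratum SD of sqrt(0.10) x 0.7 = 0.22 log10, so strata one SD either side of the mean differ about 2.8-fold in GMT (about 1.6-fold at 2%). For serogroup Y after dose 2, the corresponding rates would be about 57% and 85%. Nothing in the documents supports such spreads. Country is not a randomisation stratum, so center is still only partly used. The Day 0 titer is drawn at 42-89 days and the endpoint follows three doses at 13-19 months; values below 1:4 are set to LLOQ/2. It may predict little. The SAP already describes conduct in the past tense, so the change would come late.

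All of this stands as a limit on the size of the point, and it is why adjustment is recommended rather than required. It does not remove the point: the covariates are already collected, and the price when they explain nothing is very small. Country is a deliberate compromise against sparse center cells. A missing-baseline rule does touch the no-imputation statements in SAP 5.3.2 and Protocol 12.3.2, so it needs a line there. The Secondary Objective 1 interval also omits the Day 0 titer; the stratified interval proposed here does not address that.

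**Conclusion.** The concern holds as a recommendation. Both intervals omit the randomisation strata, and the primary one also omits an available baseline. They are nominal or mildly conservative, so any claim of non-inferiority made with them is sound. The likely benefit of adjustment is 0 to 0.9 points of overall primary power at a true ratio of 1, and up to about 5 points if all four true ratios are 0.9 and age and country explain 10%. For Secondary Objective 1 it is -0.3 to +1.6 points. These figures rest on assumed R-squared values, independent serogroups, 528 evaluable per group and an assumed layout of centers and countries. Gains beyond the strata need a prognostic Day 0 titer, which is uncertain.

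**What to change.** Before unblinding:

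- **Primary objective.** For each serogroup, fit a linear model to the log10 post-booster titer with vaccine group, age stratum, country (the five PCV10 countries, as pooled center) and the same serogroup's log10 Day 0 titer. Keep the 1/1.5 margin. Retain subjects without a valid Day 0 result by a stated rule, for example a constant value plus a missing indicator.
- **Secondary Objective 1.** Use a stratified Miettinen-Nurminen score interval with Mantel-Haenszel weights, by age or by age and country, with a prespecified collapsing rule. Name the method, since a stratified Wilson form gave no gain. Collapsing matters: for the younger age category SAP 3.2 gives "Group 1 and Group 2: approximately 144 subjects in each group", so 144 x 528/716/5 = 21.2 evaluable younger infants per group per country, and 21.2 x 0.06 = 1.3 expected serogroup C non-responders per cell if spread evenly.
- **Both.** Keep the current unadjusted intervals as supportive output and list the change in SAP 5.7.

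If unblinding has already occurred, report the adjusted results only as labelled sensitivity analyses.

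**Cost.** No new data. The work is one model statement per serogroup, edits to SAP 5.1.1.2 and 5.1.2.2, a line in SAP 5.3.2 on missing baseline, and the SAP 5.7 entry, needed because Protocol 12.1.1.2 and 12.1.2.2 fix the unadjusted methods. If the covariates explain nothing, the primary interval is 0.12% wider (0.7% with about 40 unpooled centers plus baseline) and Secondary Objective 1 loses about 0.3 points of overall power.
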